On the day of a LP, the patient may receive a pre-arranged breakfast. The patient receives a pre-arranged lunch in the late morning, to be finished by about 2 hours before the LP. On the day of a LP the patient should have no other oral intake except for medications and water before the LP. When the patient is on NAC, as soon as the lunch is finished, the patient takes 2,000 mg of NAC in water.

At about 2 hours after the pre-arranged lunch meal, a LP for research purposes is done to obtain CSF. For the LP, the subject sits upright (alternatively the subject may be lying sideway with knees curled up toward the chest). The lower back will be cleansed. For local anesthesia, lidocaine without epinephrine will be injected into and through the skin of the back. A needle will be inserted through the anesthetized skin between two lumbar vertebral processes. A total of 6 1-mL aliquots of CSF will be obtained. Each aliquot will be placed immediately on dry ice. It usually takes 5 to 10 minutes to collect the CSF. After the fluid is collected, the needle will be removed.

Flow Diagram (Inpatient Visit): A lumbar puncture (LP) is performed before and after 5 doses of N-acetylcysteine (NAC). The length of the inpatient stay at the NIH Clinical Center will depend on when during the week the patient is admitted and whether the patient has a post-spinal headache. After the second LP, the patient is observed at least overnight (discharge on Day 4). The inpatient visit may last up to 8 days, for insertion of a blood patch and observation in the event of a post-spinal headache after the second LP.

After 5 NAC doses and about 48 hours of NAC administration, the LP for research purposes is repeated. Again, the patient receives a pre-determined lunch at about 12 noon. After the second LP, the subject is observed overnight and is discharged the next day if there is no post-spinal headache.

As noted below, the lumbar puncture may be done under fluoroscopic guidance by a neuroradiologist in the X-ray department.

In HVs, LPs are done also at about 2 hours after ingestion of a pre-determined meal. NAC is not given.

4.D.5. N-Acetylcysteine: In patients, beginning after the first LP, N-acetylcysteine (NAC) is begun at a 2,000 mg by mouth twice daily. HVs do not receive NAC.

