4.D.6. Radiation (fluoroscopy): If technical difficulty is experienced or anticipated, the LP may be done under fluoroscopic guidance by a neuroradiologist, for research purposes. The anticipated Effective Dose is 0.023 rem per fluoroscopy (up to 2 fluoroscopies). The radiation exposure is for research purposes only.

In the event of a post-spinal headache after the first LP, a blood patch is inserted by an anesthesiologist, the patient is observed as an inpatient as needed until the headache is resolved, and the patient is then discharged and withdrawn from the study.

In the event of a post-spinal headache after the second LP, a blood patch is inserted by an anesthesiologist, the patient is observed as an inpatient as needed until the headache is resolved, and the patient is then discharged from the study.

4.E. End of participation: At the end of study participation the patient is transferred to the care of his or her primary physician or neurologist. There is no medical care offered at completion of study procedures. There are no follow-up visits under this protocol

After completing study participation, the patient will receive a letter summarizing the results of the research tests they underwent and their interpretation, recognizing that the data should not be used for clinical diagnosis or management purposes. The patient will be free to share the letter with health care providers; however, the letter will be mailed only to the patient. HVs do not receive summary letters describing their research results.

5. Management of Data and Samples

Data from this study will be entered in spreadsheets of the Clinical Neurocardiology Section (CNCS) or onto the Section's clinical research FileMaker Pro database, until the planned CTDB database under construction for the CNCS is active.

5.A Storage: In this study, CSF samples are obtained and stored for neurochemical assays. The sample tubes are labeled coded without personal identifying information. The coded samples are stored in locked freezers of the Clinical Neurocardiology Section (CNCS). Residual samples will continue to be stored, so that groups of samples can be re-analyzed as needed.

5.A.1. Future use: The Consent Forms state that the subject allows future use of his/her data and samples by the Clinical Neurocardiology Section (CNCS) or other components of intramural NIH. If the subject does not wish to have his/her data and samples used in future studies, the subject should not participate.

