5.A.2. Transfer to Repository Protocol 08-N-N090: Upon termination of this protocol data and samples will be transferred to repository protocol No. 08-N-N090. Data without personal identifying information will continue to be stored on secured computers, on encrypted electronic media, or in notebooks of the CNCS. Coded samples will continue be stored in locked freezers of the CNCS. Personnel of the CNCS will have access to the stored samples and data. Any loss or destruction of stored data or samples will be reported to the IRB.

5.B. Data and sample sharing plan

This protocol is not subject to the Genomic Data Sharing (GDS) policy.

The Consent Forms state that the samples and data will not be shared with those outside NIH or a non-NIH repository.

6. Additional Considerations

6.A. Research with investigational drugs or devices: This study does not involve an investigational drug or device.

6.A.1. N-Acetylcysteine (NAC): will be obtained from a commercial supplier of NAC. The obtained NAC will be assayed and a Certificate of Analysis obtained before the NAC is administered. NAC will be dispensed through the NIH Clinical Center Pharmacy Department.

6.A.2. MAO inhibitor: The prescribed MAO inhibitor the patient takes will be identified by the NIH Clinical Center Pharmacy Department and dispensed by inpatient nursing personnel.

6.B. Gene therapy: This study does not involve gene therapy.

7. Risks and Discomforts An admission history and physical examination are done. This does not involve risk.

7.A. History and physical examination: Having a history and physical examination done does not involve increased medical risk.

7.B. Venipuncture: There may be some discomfort and bruising from the needle insertion. Some people feel light-headed or faint.

7.C. Blood drawing: The amount of blood to be drawn for laboratory tests (up to about 30 mL) should not involve increased medical risk.

7.B. Lumbar puncture: Lumbar puncture may produce brief pain or a tingling sensation in the legs if the needle brushes against a nerve. If this happens, the needle will be adjusted. There may be a mild backache at the site of needle insertion. About one-third of people have a headache for a few days after a lumbar puncture. In the event of a post-spinal headache a blood patch will be inserted by an anesthesiologist.

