The written summary will be signed by the investigator obtaining consent and a witness to the oral presentation. The short written consent form will be signed by the participant and a witness who observed the presentation of information. The interpreter may sign the consent document as the witness and, in this case, will note “Interpreter” under the signature line. A copy of the signed form will be provided to the participant to take home.

The investigator obtaining consent will document the consent process in the participant’s medical record, including the name of the interpreter. Further, all instances of use of the short form process will be reported to the IRB at the time of continuing review. If the Clinical Center Short Written Consent form is used three times or more for the same language within an IRB approval period, this will be reported to the IRB immediately.

Interpreters will also be present for the other protocol procedures as necessary.

15. Data and Safety Monitoring

15. Data and Safety Monitoring

15.A. Data and safety monitor: Data and safety will be monitored by the PI.

15.B. Data and safety monitoring plan: Parameters to be monitored are those in the appended **Clinical Investigation Monitoring Form (Appendix 25.I)**. At the end of study participation, for each protocol participant, the Clinical Investigation Monitoring Form is completed and signed by the PI. Data and safety monitoring is conducted at the time of de-briefing of each protocol subject prior to discharge. Data and safety monitoring for the entire study is conducted via review by the PI of the notebook containing the Clinical Investigation Monitoring Forms at 6-month intervals beginning from the date of de-briefing of the first protocol participant.

15.C. Criteria for stopping the study or suspending enrollment or procedures: The study will be stopped if 2 of the same Serious Adverse Events occur related to NAC administration.

16. Quality Assurance (QA)

16.A. Quality assurance monitor: The PI and NINDS Quality Assurance Audit Committee will monitor the study.

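### A headache that starts after discharge from the second lumbar puncture has no scheduled means of being detected, and the blood-patch sentence does not say how it would be handled

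*Combined protocol and SAP*

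**What the plan says.** **The risk.** Section 7.B (Lumbar puncture) gives the rate: "About one-third of people have a headache for a few days after a lumbar puncture". It continues, with no time limit: "In the event of a post-spinal headache a blood patch will be inserted by an anesthesiologist". Section 8.C names the development of a post-spinal headache among the things to be monitored.

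**Observation after the second LP.** Section 4.D.4 makes next-day discharge conditional: "After the second LP, the subject is observed overnight and is discharged the next day if there is no post-spinal headache". The flow-diagram text in the same section sets overnight as a minimum, with discharge on Day 4, and allows a longer stay: "The inpatient visit may last up to 8 days, for insertion of a blood patch and observation in the event of a post-spinal headache". The headache paragraphs under 4.D.6 add: "In the event of a post-spinal headache after the second LP, a blood patch is inserted by an anesthesiologist". The patient then remains an inpatient as needed until the headache has resolved.

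**Safety collection.** Section 8.C schedules symptom queries at morning rounds on Day 2 and Day 3, during NAC treatment. Section 15.B fixes the later collection: "Data and safety monitoring is conducted at the time of de-briefing of each protocol subject prior to discharge".

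**After discharge.** Sections 4.A.1, 4.A.2 and 4.E provide no follow-up visits for patients or healthy volunteers. Section 4.E passes the patient to his or her own physician and states: "There is no medical care offered at completion of study procedures". Section 17 makes the Principal Investigator responsible for detecting, documenting and reporting adverse events. It sets no end date at discharge, and its reporting clocks start when the investigator first learns of an event.

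**The concern.** Headache is the only LP effect to which the protocol attaches a rate, and that rate is high. The scheduled means of finding it stop less than a day after the second LP if discharge is in the morning. A participant who is well at de-briefing and has a headache later is not asked about it by anyone. The event enters the record only if the participant volunteers it.

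Two things are at stake. The first is how complete the safety record is for a study that Section 13 classes as more than minimal risk and that includes healthy volunteers having two research LPs each. The second is clarity. Section 7.B speaks of a blood patch without limit of time and Section 4.E says no care is offered at completion, so the documents do not say what happens when a headache is reported from home.

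**Working it through.** The one-third rate is a stated background figure. The protocol derives no event count or sample size from it, so there is nothing to reproduce. The check is a timeline followed by a bound.

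**1. Timeline on the shortest schedule.**
- Discharge is on Day 4, the day after the second LP (4.D.4), so the second LP is on Day 3.
- About 48 hours and 5 NAC doses separate the LPs (4.D.4), so the first LP is on Day 1.
- Lunch is at about noon and the LP about 2 hours later (4.D.4), so the second LP is at about 14:00 on Day 3.
- The symptom queries are on the mornings of Day 2 and Day 3 (8.C). Both come before the second LP.
- The only scheduled collection left after the second LP is the de-briefing before discharge (15.B).

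**2. Length of observation if no headache appears.** The discharge hour is not stated; assume 08:00 to 12:00 on Day 4.
- From 14:00 to midnight is 10 hours.
- 10 + 8 = 18 hours; 10 + 12 = 22 hours.

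**3. Headaches expected per LP at the stated rate,** n × 1/3:
- 10 patients (target completers, 3.A2): 3.3
- 15 patients (planned for inpatient testing, 10.C): 5.0
- 35 patients (ceiling, 10.C): 11.7
- 6 healthy volunteers (3.A2): 2.0

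**4. Headaches starting after discharge.** Let f be the share that start after discharge. The expected number is n × 1/3 × f. The documents give no value for f, because 7.B says how long a headache lasts and not when it begins.

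| n | f = 0 | f = 0.25 | f = 0.5 | f = 1 |
|---|---|---|---|---|
| 10 | 0 | 0.8 | 1.7 | 3.3 |
| 35 | 0 | 2.9 | 5.8 | 11.7 |

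The columns illustrate the range and do not estimate it. At f = 0 nothing is lost.

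**5. Limits of the rate.** Section 4.D.6 withdraws patients who have a post-spinal headache after the first LP. Those who reach the second LP are therefore a selected group, and one-third need not apply to them. Section 7.B also counts headaches in general, while 8.E refers to post-spinal headaches that require a blood patch. For healthy volunteers the documents give no discharge time after the second LP, so the 18 to 22 hours apply to patients only.

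**The case against.** The strongest reply is that the protocol manages post-LP headache with some care. Discharge is conditional, overnight is a minimum, the stay can extend to 8 days, and a headache that appears in hospital is treated and followed until it resolves. Section 17 does not close the adverse-event record at discharge, and patients are handed over to a physician. All of this stands, and it confines the point to headaches that start after discharge.

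A reader might infer more than the documents support:

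- *That all safety collection ends at discharge.* Only scheduled collection ends. An unprompted report can still be recorded under Section 17, but nothing prompts it.
- *That the blood-patch sentence cannot be carried out.* It can be for any headache that appears in hospital. Sections 7.B and 4.E can be read in sequence, one during participation and one after it. What is missing is a described route for a headache reported later.
- *That a known number of headaches will be missed.* The few days in 7.B are a duration. Treating them as an onset window has no basis in the text.
- *That the data will make the second LP look safer than the first.* Follow-up is indeed unequal: about 48 inpatient hours with two scheduled queries after the first LP, and as little as one night after the second. But no such comparison is planned, and withdrawal for headache after the first LP would confound it anyway.

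Finally, the consent forms and the contents of the Clinical Investigation Monitoring Form (25.I) were not available for this review. Discharge instructions or a call-back number may be there. They would help a participant who calls, but 15.B would still place the scheduled collection before discharge.

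**Conclusion.** The concern holds as a gap in active detection. For a patient without a headache, scheduled safety collection ends about 18 to 22 hours after the second LP (morning discharge assumed), and no later contact to ask about symptoms is described for patients or healthy volunteers. The number of headaches missed lies between none and all of those that occur, and the documents do not allow a narrower statement. The primary CSF analysis is unaffected. This is an inexpensive improvement to safety capture, together with two passages that need reconciling.

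**What to change.** 1. In Sections 8.B/8.C and 15.B, extend adverse-event collection past discharge for both patients and healthy volunteers. Use one scheduled telephone contact by existing study staff a few days after the second LP, asking about headache and any other new symptom.
2. Complete and sign the Clinical Investigation Monitoring Form (25.I) after that contact.
3. Reconcile the open-ended blood-patch sentence in 7.B with the end-of-participation text in 4.E, so that the documents say how a headache reported after discharge is handled. The clinical rule is for the sponsor to decide.

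**Cost.** A short amendment and at most 35 + 6 = 41 calls, with no extra visit. Forms would be signed a few days later, and the reported headache rate may rise because more of the events are found.

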7.C. N-Acetylcysteine: NAC is likely safe for most adults, when used as a prescription medication. It can cause gastrointestinal side effects such as nausea or abdominal pain, as well as headache and hypersensitivity reactions. Based on the mechanism of anti-oxidant effects of NAC, no potential drug interactions would be anticipated in PD patients on an MAO inhibitor.

We anticipate that gastrointestinal side effects will be dose-related. If these symptoms occur at the initial dose, they will be considered to be expected non-serious adverse events and reported as such, and the dose will be decreased by one-half. If the symptoms occur at the lower dose, then the NAC will be stopped, the patient will be withdrawn from the study, and the patient will be observed as an inpatient until the symptoms resolve.

Rarely, NAC can cause rashes, fever, headache, drowsiness, low blood pressure, or liver problems. If a patient experiences these symptoms or signs or others that in the opinion of the Principal Investigator are the result of NAC, the patient will be withdrawn from the study.

7.D. Radiation (fluoroscopy): This research study involves exposure to radiation from fluoroscopy if technical difficulty is anticipated or experienced with the lumbar puncture. This radiation exposure is not required for medical care and is for research purposes only. The estimated Effective Dose, **0.05 rem** (2 fluoroscopy procedures), is below the guideline of 5 rem per year allowed for research subjects by the NIH Radiation Safety Committee.

There is no direct evidence that the amount of exposure received from participating in this study is harmful. Pregnancy or lactation are exclusionary in this study.

8. Subject Safety Monitoring

8A. Identify monitors during participation in study procedures: In this study the monitors during participation in study procedures are the Principal Investigator, Research Nurse, or Nurse Practitioner.

8.B. Parameters to be monitored: The parameters to be monitored include symptoms and signs. During all study procedures, subjects are monitored by clinically credentialed personnel of the Clinical Neurocardiology Section (Physician, Registered Nurse, or Nurse Practitioner) or authorized personnel of the NIH Clinical Center (e.g., neuroradiologist).

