8.C. Toxicity criteria to be used: The Protocol requires monitoring of procedures and possible symptomatic side effects of NAC or the development of a post-spinal headache. The NIH's Common Terminology Criteria for Adverse Events (version 4.0) will be used. The patient is queried about any new symptoms at morning rounds on Day 2 and Day 3 during NAC treatment. If the patient reports gastrointestinal side effects at the initial dose, the dose will be halved. All procedures involving more than minimal anticipated risk are administered only by experienced, qualified personnel or personnel.

8.D. Criteria for stopping individual procedures: The PI has the discretion of stopping individual procedures if the medical or psychological risk outweighs the anticipated scientific benefit.

8.E. Criteria for individual subject withdrawal: If a patient develops a post-spinal headache requiring a blood patch, the subject is withdrawn. Subjects may refuse certain tests or procedures, or may withdraw from participation early, without loss of benefits to which they were previously entitled. The Principal Investigator may also exclude a subject from further participation, such as in the event of known or suspect falsification of medical history information or refusal to undergo planned tests or procedures, without loss of benefits to which the subject was previously entitled. If NAC at the initial dose produces gastrointestinal symptoms, the dose will be halved; and if the gastrointestinal symptoms persist after decreasing the NAC dose, then the patient will be withdrawn from the study. If a patient experiences other symptoms that in the opinion of the Principal Investigator are the result of NAC, the patient may be withdrawn from the study. If a woman becomes pregnant while on study, she will be withdrawn.

8.E.1. Withdrawal definition: For record-keeping purposes, "withdrawal" refers to cessation from any further participation in the study, based on the decision of the participant or the Principal Investigator, before the endpoint for participation has been reached. The endpoint for participation is after obtaining CSF while the patient is on N-acetylcysteine. Reaching the study endpoint for participation does not constitute withdrawal.

9. Outcome Measures

In this study outcome is not related to measures of symptoms or signs or a disease but to CSF neurochemical findings.

9.A. Primary outcome measure

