16.B. Quality assurance plan: This protocol will undergo periodic review by the NINDS Quality Assurance (QA) Audit Committee as outlined in the NINDS QA Standard Operating Procedure (SOP). The purpose of the QA audit is to assess compliance with applicable regulatory requirement, good clinical practice guidelines, and NINDS policy, as well as to provide recommendations for improving the management of clinical research data. The protocol will be audited according to the decision algorithm as described in the NINDS SOP. Since the study involves more than minimal risk, the protocol will undergo an audit during the first year and then a minimum of every 3 years thereafter.

17. Reporting of Unanticipated Problems, Adverse Events and Protocol Deviations

The Principal Investigator is responsible for detecting, documenting, and reporting unanticipated problems, adverse events (AEs), including serious adverse events (SAEs), and deviations in accordance with NIH policy, IRB requirements, and federal regulations. Relatedness to the research of all serious adverse events will be determined by the PI in consultation with the CD.

Serious unanticipated problems and serious protocol deviations will be reported to the IRB and CD as soon as possible and in writing not more than 7 days after the PI first learns of the event. Not serious unanticipated problems and not serious deviations will be reported to the IRB and CD as soon as possible and in writing not more than 14 days after the PI first learns of the event. Written reports will be submitted in PTMS.

Deaths will be reported to the Clinical Director within 7 days after the PI first learns of the event.

All adverse events, deviations, and unanticipated problems will be summarized and reported at the time of Continuing Review.

For reporting purposes, toxicity criteria in the Common Terminology Criteria for Adverse Events (CTCAE) will be used.

18. Alternatives to Participation

In this study, subjects do not receive any treatment to treat symptoms of PD or forego any treatment in order to participate in this study. The alternative, therefore, is not to participate.

The patients will be taking an MAO inhibitor under the care of their own physicians.

NAC is marketed in the United States as a dietary supplement. Patients can take NAC on their own.

19. Privacy

All research activities will be conducted in as private a setting as possible.

20. Confidentiality

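### Section 7.C labels every gastrointestinal symptom at the initial NAC dose non-serious in advance, which conflicts with the serious-event duty in section 17

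*Combined protocol and SAP*

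**What the plan says.** Five places in the combined protocol and SAP bear on this. The number 7.C is used twice; the N-Acetylcysteine paragraph is meant throughout.

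- **7.C, initial dose.** After naming nausea and abdominal pain as examples, the protocol states: "We anticipate that gastrointestinal side effects will be dose-related". It then says: "If these symptoms occur at the initial dose, they will be considered to be expected non-serious adverse events and reported as such". The same sentence goes on to the dose reduction.
- **7.C, lower dose and other reactions.** "If the symptoms occur at the lower dose, then the NAC will be stopped, the patient will be withdrawn from the study". A separate paragraph begins: "Rarely, NAC can cause rashes, fever, headache, drowsiness, low blood pressure, or liver problems". Neither carries a seriousness label.
- **8.C, toxicity criteria.** "The NIH's Common Terminology Criteria for Adverse Events (version 4.0) will be used".
- **15.C, study stopping rule.** "The study will be stopped if 2 of the same Serious Adverse Events occur related to NAC administration". It is the only study-level stopping rule in the text available.
- **17, reporting.** The PI must look for events and record them, and the duty extends to "reporting unanticipated problems, adverse events (AEs), including serious adverse events (SAEs), and deviations in accordance with NIH policy, IRB requirements, and federal regulations". On who judges the link to the research, the section says: "Relatedness to the research of all serious adverse events will be determined by the PI in consultation with the CD".

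**The concern.** The 7.C sentence does two things at once. Calling GI symptoms *expected* is legitimate in a protocol, because expectedness is a property of a type of event given what is known about the drug. Calling them *non-serious* is different. Seriousness is a property of one event in one patient and can be judged only once the event has occurred. Because the sentence also says how these events are to be reported, it reads as an instruction to staff and not only as a description of the usual case.

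The label also sits where the protocol itself expects GI toxicity to be greatest. It calls these effects dose-related, and within a patient the initial dose is the higher of the two dose levels that 7.C describes. The stopping rule and the relatedness review both start from the word *serious*, so an event filed as non-serious reaches neither.

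**Working it through.** No sample size, power or error rate is in dispute, so the plan has no figure to reproduce. The check sets the passages side by side.

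**Step 1. Scope of the label.**

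| Event | Advance seriousness label in 7.C? |
|---|---|
| GI symptoms, initial dose | Yes: expected and non-serious, no condition |
| GI symptoms, halved dose | No |
| Rash, fever, low blood pressure, liver problems and similar | No |

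The label covers one row only.

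**Step 2. One hypothetical event under each passage.** Take a GI event at the initial dose that meets ordinary criteria for a serious event.

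| Question | 7.C taken literally | Section 17 taken literally |
|---|---|---|
| Recorded as an SAE? | No | Yes |
| Relatedness judged by the PI with the Clinical Director? | Not triggered | Required |
| Can count under 15.C? | No | Yes, if related to NAC |
| In the Continuing Review summary? | Yes, as an adverse event | Yes |

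The two passages give different answers in the first three rows. 7.C is the more specific text and section 17 the more general duty. Nothing states which governs, and the text available does not define a Serious Adverse Event. Two staff members could each follow the protocol and file the same event differently. Deaths are a partial exception, since section 17 requires them to be reported to the Clinical Director separately.

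**Step 3. Does CTCAE settle it?** No. CTCAE grades severity, and severity is not seriousness. Section 8.C neither contradicts the 7.C label nor overrides it.

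**Step 4. Can the effect be sized?** The relevant input is the per-patient rate *p* of a NAC-related serious GI event of the same kind at the initial dose. The documents give none. Section 10.C plans 15 patients for inpatient testing in the main study. If such events were counted, the chance of reaching two would be

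P(at least 2) = 1 − (1 − p)^15 − 15p(1 − p)^14.

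- Assumed p = 1%: 1 − 0.860 − 0.130 = 0.010.
- Assumed p = 10%: 1 − 0.206 − 0.343 = 0.451.

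Both rates are assumptions, and the result moves from negligible to near even odds between them. This shows why no magnitude can be claimed; it does not estimate one.

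**The case against.** The best defence is that section 17 already controls. It covers all SAEs under NIH policy, IRB requirements and federal regulations, and has no GI exception. A sentence under Risks and Discomforts would not normally be read as overriding the reporting section. The examples in 7.C are mild, and the patient continues on half the dose, so the drafters probably had the ordinary tolerable case in mind. That is a fair reading of intent. It means the consequences arise only if 7.C is applied literally. It does not remove the conflict, because the 7.C wording is unconditional and no order of precedence is given.

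Several stronger readings are tempting, and the documents do not support them:

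- *GI toxicity from NAC can never be recorded as serious or count toward stopping.* The label stops at the initial dose. Events at the halved dose can be SAEs and can count under 15.C, and section 17 applies throughout.
- *7.C contradicts its own provisions for stopping NAC, withdrawal and inpatient observation.* Those steps belong to symptoms at the lower dose, which are not pre-labelled. Patients are in any case already inpatients by design.
- *7.C conflicts with the use of CTCAE.* An event can be graded by CTCAE whatever its seriousness label.
- *A definite number of patients is lost from the stopping count.* Any such number would rest on an assumed rate of GI symptoms of any grade, which says nothing about serious ones.

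**Conclusion.** The point holds in limited form. Section 7.C fixes the seriousness of initial-dose GI events in advance, without regard to severity or outcome, and this conflicts with the SAE duty in section 17. If staff follow 7.C literally, a serious event of this kind would be misfiled, would bypass the relatedness review and would not count under 15.C. If they follow section 17, none of this happens.

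The conclusion rests on the wording alone. It assumes only that a GI event at the initial dose could meet criteria for seriousness. It does not assume that such events are likely. The size is unknown, since the documents give no rate of serious GI events. The point merits correction because the affected text feeds a safety rule and the edit is small.

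**What to change.** Change the one sentence in 7.C. Keep *expected*, delete the advance *non-serious* label, and say in substance: *the seriousness of each event is assessed individually, its severity is graded by CTCAE version 4.0, and it is reported under section 17.*

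No change is needed in 15.C. It already counts any NAC-related SAE without excluding GI events, so it works as written once 7.C is corrected. The dosing and withdrawal steps in 7.C are outside this point and stay untouched.

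The cost is one sentence, with no added procedure, sample or visit. The downside is that the reported SAE count could be higher, and a GI event judged serious and related to NAC would then count toward stopping.
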